6.1 Definition of Adverse Event

An adverse event (AE) is any noxious, pathologic, or unintended change in anatomical, physiologic, or metabolic function, as indicated by physical signs, symptoms, or laboratory changes occurring in any phase of the clinical trial, whether associated with study medications or placebo, and whether or not considered related to the study medications.

Adverse events include, but are not limited to:

1. Worsening (change in nature, severity, or frequency) of conditions present at the start of the trial.
2. Acute illness occurring during the trial.
3. Drug reactions.
4. Experiences related or possibly related to concomitant medications.
5. Clinically significant abnormalities in physical examination, vital signs, or laboratory values (examination of laboratory values will not be done on a routine basis during study visits, but may be performed if any concern for adverse event arises).

6.2 Serious Adverse Events

In general, serious adverse events are not expected with the use of these over the counter dietary supplements. However, if a serious adverse event does occur, the Principal Investigator report all serious adverse events (SAEs) that are unexpected (not listed in the most up-to-date Physician's Desk Reference) and potentially related to the study medication to the DSMB within two to three business days after becoming aware of the event. The study investigators will also conform to the AE and SAE reporting requirements of the IRB and the Research and Development Committee of the Atlanta VA.

6.3 Describing Adverse Events and Serious Adverse Events

The Principal Investigator will make a determination on reporting the relationship of the adverse event to study medication as one of the following:

- **None:** Unrelated to study medication
- **Possible:** Possible association with study medication is known
- **Probable:** Study medication has a known association with this type of event, and the event in question is probably due to the medication
- **Definite:** Study medication has a known association with this type of event, and the event in question is definitely due to the medication

The Principal Investigator will also make a determination of the severity of the adverse event as one of the following:

- **Mild:** No limitation of usual activities
- **Moderate:** Some limitation of usual activities
- **Severe:** Effects ranging from inability to carry out usual activities to life-threatening.

7. Trial Termination

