9.1 Data and Safety Monitoring Board (DSMB)

An independent Data and Safety Monitoring Board (DSMB) will be appointed and charged with oversight responsibility for the performance and safety of the trial. The board will be comprised of three members (including a statistician) with clinical trial experience. An independent, experienced physician with no involvement in the study will serve as the chairman of the board. They will meet formally prior to the study to approve the protocol and thereafter convene about every six months or more frequently as needed. In general, the DSMB will receive reports comprised of: (1) the number of subjects that have signed consent, (2) number of screen fails, (3) number of drop-outs, (4) number of completers, (5) listing of reasons for drop-out, (6) a tabulated list of all adverse events, their frequency and severity, that occur during the study, (7) complete description on an IRB template of all serious adverse events that occur during the study, and (8) a written description of any known breaches of confidentiality of study subjects.

After each meeting, the DSMB will make formal recommendations regarding trial continuation. As there are no interim analyses, there will be no grounds for stopping the trial early for efficacy. However, the trial may be stopped early for any safety or performance issues. A special responsibility of the DSMB is to review serious adverse events (SAEs) as defined in this protocol. SAEs considered reportable per the Reportable Events policy will be reported to the chairman of the DSMB or designee within 48–72 hours for review. This initial review will determine whether there is a recommendation for a change in the protocol (or halt the study) until the matter can be considered by a quorum of the DSMB. All SAEs (reportable and non-reportable) SAEs will be available for review at the semi-annual DSMB meetings.

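### Every causality grade above None in section 6.3 is worded around an association already known, so a suspected new reaction has no fitting grade and its prompt reporting under section 6.2 is put at risk

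*Combined protocol and SAP*

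**What the plan says.** Section 6.3, which covers both adverse events and serious adverse events, requires the Principal Investigator to assign one of four relationship grades. The lowest, *None*, is for an event judged to have no relationship with the treatment. The second, *Possible*, is worded "Possible association with study medication is known". The third, *Probable*, carries two conditions: "Study medication has a known association with this type of event, and the event in question is probably due to the medication". The fourth, *Definite*, keeps the first of those conditions and replaces probable cause with definite cause.

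Section 6.2 has the Principal Investigator send to the DSMB, within 2–3 business days of learning of them, serious adverse events that are "unexpected (not listed in the most up-to-date Physician's Desk Reference) and potentially related to the study medication". It adds that the reporting requirements of the IRB and the VA Research and Development Committee also apply.

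Section 9.1 gives a second route: "SAEs considered reportable per the Reportable Events policy will be reported to the chairman of the DSMB or designee within 48–72 hours for review". It also makes every SAE, reportable or not, open to DSMB review at meetings held about every six months, or more often if needed.

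**The concern.** A causality grade should record how likely it is that the study medication caused this event in this participant. Whether such an event has been seen before with the product is a different question, normally handled as expectedness. Section 6.3 merges the two by building prior knowledge into each grade above *None*.

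The prompt-reporting rule in section 6.2 is aimed at events that are not listed. Those are the events least likely to have an established association, and so the ones the scale handles worst. The investigator who suspects something new must either choose a grade whose definition is not met or record the event as unrelated.

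At stake is whether the trial's only stated relatedness assessment can register a new reaction, and whether a serious one reaches the DSMB in days.

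**Working it through.** No arithmetic on power, error rate or sample size applies, and the plan gives no figure to reproduce. The check sets the definitions side by side.

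**Step 1. Does any grade fit a suspected reaction with no previously known association?**

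| Grade (6.3) | What the wording turns on | Fits? |
|---|---|---|
| *None* | A judgement that the event is unrelated | No, because the investigator suspects the medication |
| *Possible* | A possible association that is known | No on its plain wording; yes only on a looser reading |
| *Probable* | A known association, plus probable cause in this case | No |
| *Definite* | A known association, plus definite cause in this case | No |

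Three of the four grades carry the prior-knowledge condition, two of them beyond dispute. The fourth says the opposite of what the investigator believes. The text leaves a gap. *None* is the only grade not worded around prior knowledge, so a forced choice may fall there.

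**Step 2. How does this meet the section 6.2 rule?** Cross the two kinds of prior knowledge for a serious event the investigator suspects:

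| Association known? | Listed in the reference? | Grade available above *None*? | Prompt under 6.2? |
|---|---|---|---|
| Yes | Yes | Yes | No, because it is expected |
| Yes | No | Yes | Yes |
| No | No | None that fits on plain wording | Depends on step 3 |

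The remaining combination, listed but not known, is in practice empty. The second row shows that known and listed are different tests, so the two sections pull against each other without strictly excluding each other.

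**Step 3. The third row turns on how *potentially related* is decided.**

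- Judged directly, without the scale: the event meets section 6.2 as written and goes to the DSMB in 2–3 business days.
- Judged by the section 6.3 grade, with *Possible* read loosely: the same result.
- Judged by the section 6.3 grade, with the definitions read strictly and the event placed in *None*: it is not sent promptly under section 6.2.

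The protocol does not say which applies. The third course is easy to take, because section 6.3 is the only relatedness scale given and the same person makes both decisions.

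**Step 4. What do the other routes do?** The section 9.1 route does not mention the causality grade, but it depends on a policy whose criteria the protocol does not set out. The same holds for IRB and Research and Development Committee requirements. Either may catch the event; neither can be shown from the documents to do so. The one DSMB route that clearly needs no judgement of relatedness or reportability is the periodic review.

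**Step 5. Do sections 6.2 and 9.1 agree with each other?** Not fully. One uses unlisted plus potentially related; the other uses the Reportable Events policy. One clock runs in business days and the other in hours. Three business days from a Friday end on the following Wednesday, which is 5 × 24 = 120 hours against an upper limit of 72.

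**The case against.** The strongest reply is that this is loose drafting with no necessary consequence. *None* is a positive finding of no relationship, and an investigator who suspects the medication cannot honestly select it. *Possible* omits the phrase about the type of event that the two higher grades contain, so it can be read as a possible link recognised in the case at hand. Section 6.2 does not refer to the grades at all, and other reporting routes exist.

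Much of this stands, and it rules out several stronger conclusions that a reader might infer:

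- *That a new reaction must be graded None.* The text leaves a gap; it does not compel that grade.
- *That a new serious reaction is never promptly reported, or waits up to six months.* Section 6.2 as written covers an unlisted event judged potentially related, section 9.1 adds its own route, and the DSMB may meet between scheduled meetings.
- *That such events would be tabulated for the DSMB as unrelated.* Section 9.1 describes a table of all adverse events by frequency and severity, with a full description of each SAE. Relatedness is not among the listed contents.
- *That many later participants would be exposed first.* Treatment lasts about two weeks, but no accrual rate is given.
- *That the protocol says there is no trial experience bearing on the safety of the combination in this population.* The background speaks only of trials of lung health effects of zinc or antioxidant supplements. It does not address safety experience or the combination.

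The prompt rule in section 6.2 also covers serious events only, so a non-serious new reaction falls outside it however it is graded.

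What the reply does not remove is the definitions themselves. *Probable* and *Definite* are closed to a new reaction on any reading, however strong the evidence in the case. *Possible* is open only if its wording is relaxed.

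**Conclusion.** The point holds as a fault in a stated rule. Section 6.3 has no fitting grade for a suspected but previously unknown reaction, explicitly so for *Probable* and *Definite* and on plain wording for *Possible*. Under-grading as unrelated is a risk. Failure to report promptly under section 6.2 is a further risk, conditional on the investigator using the section 6.3 grade to decide what is *potentially related*. The documents neither state nor exclude that link.

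The size cannot be put as a number of events or a length of delay. That would need an event rate, an accrual rate and the content of the Reportable Events policy, none of which the documents give. The efficacy analysis is unaffected. The change should be made because it bears on safety oversight and needs only rewording.

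**What to change.** 1. In section 6.3, define the grades by the evidence for causation in the individual case, such as timing relative to dosing, plausibility, alternative causes and the course after exposure ends. Remove known association as a condition. One workable form is *None* for an event clearly due to another cause and *Possible* where a causal relation cannot be excluded; other standard scales would serve.
2. Leave whether an event is known or listed to the expectedness test in section 6.2.
3. State in section 6.2 that *Possible*, *Probable* and *Definite* all count as potentially related.
4. Reconcile the criteria and time limits of sections 6.2 and 9.1, so that one rule and one clock govern prompt reporting to the DSMB.

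The cost is revised wording in the protocol and case report form. A few more events are likely to be graded *Possible* and reported promptly, which means slightly more work for the investigator and the DSMB.

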7.1 Trial Termination

Termination of the trial may be recommended by Data and Safety Monitoring Board during one of their bi-annual meetings if there are concerns regarding safety or if the trial has failed to reach its declared goals.

7.2 Withdrawal of Consent

Participants who withdraw their consent during the course of the trial will discontinue their study medications and follow-up visits, but they will receive phone-call follow to monitor for adverse events and ensure appropriate safety surveillance.

The primary investigator will retain the right to withdraw a subject for any clinical/safety concerns or non-adherence to study protocol.

8. Data Collection and Statistical Considerations

Demographic data will be collected from patients undergoing initial screening for the study. During the study, we will collect data from enrolled subjects from blood samples, exhaled breath condensate and BAL fluid that are collected. The information collected for this trial will be recorded on Case Report Forms (CRFs) and entered in a web-based database called REDCAP. REDCAP is a secure, HIPAA-compliant, data management software website that requires appropriate VA credentials for access. All data entered in the REDCAP database will reside on VA servers.

For data analysis, the VINCI (VA Informatics and Computing Infrastructure) Workspace will be utilized. The VINCI Workspace will allow the team access to SAS (Statistical Analysis Software) while keeping all data on the VA's secured servers, thereby ensuring Veterans' privacy and data security.

9. Trial Administration

9.1 Data and Safety Monitoring Board (DSMB)

An independent Data and Safety Monitoring Board (DSMB) will be appointed and charged with oversight responsibility for the performance and safety of the trial. The board will be comprised of three members (including a statistician) with clinical trial experience. An independent, experienced physician with no involvement in the study will serve as the chairman of the board. They will meet formally prior to the study to approve the protocol and thereafter convene about every six months or more frequently as needed. In general, the DSMB will receive reports comprised of: (1) the number of subjects that have signed consent, (2) number of screen fails, (3) number of drop-outs, (4) number of completers, (5) listing of reasons for drop-out, (6) a tabulated list of all adverse events, their frequency and severity, that occur during the study, (7) complete description on an IRB template of all serious adverse events that occur during the study, and (8) a written description of any known breaches of confidentiality of study subjects.

After each meeting, the DSMB will make formal recommendations regarding trial continuation. As there are no interim analyses, there will be no grounds for stopping the trial early for efficacy. However, the trial may be stopped early for any safety or performance issues. A special responsibility of the DSMB is to review serious adverse events (SAEs) as defined in this protocol. SAEs considered reportable per the Reportable Events policy will be reported to the chairman of the DSMB or designee within 48–72 hours for review. This initial review will determine whether there is a recommendation for a change in the protocol (or halt the study) until the matter can be considered by a quorum of the DSMB. All SAEs (reportable and non-reportable) SAEs will be available for review at the semi-annual DSMB meetings.

9.2 Institutional Review Board Approval

The Principal Investigator is responsible for obtaining and maintaining IRB approval throughout the entire course of this study.

9.3 VA Research and Development Committee Approval

In addition to IRB approval, the Principal Investigator will ensure that the Research and Development Committee at the Atlanta VA Medical Center approves the study and receives notification of IRB approval along with letters of approval for all amendments to the study per VA guidelines.

9.4 ClinicalTrials.gov Registration

This application includes a trial which requires registration in ClinicalTrials.gov. This registration will occur prior to study initiation.

9.5 Trial Documentation

All worksheets, supporting source documents and administrative records will be retained by the Principal Investigator for a minimum of two years following the last notification of approval by an appropriate regulatory authority. The consent forms and other research documents are scanned permanently into the medical record for veteran participants of the study per usual VA protocol.

9.6 Confidentiality

9.6.1 Patient Anonymity/Protected Health Information (PHI)

All PHI collected and processed for the purposes of this study will be managed by the investigators and study staff. The anonymity of participating patients will be strictly maintained. All subjects are identified by an assigned unique patient ID number on all worksheets, CRFs, and other documents. Documents that identify the patient and contain PHI (e.g., the signed informed consent form) will be maintained in strict confidence by the study investigators and study coordinator, except to the extent necessary to allow auditing by the appropriate regulatory authority. All electronic documents containing patient information will be stored electronically on VA-encrypted drives. All data collected as a hard copy will be kept in a locked file cabinet in a locked office. Only the investigators and study staff will have access to this information.

Auditors and other authorized agents as well as that of any other applicable government agencies will be granted direct access to the study subjects' original medical records for verification of clinical trial procedures and/or data, without violating the confidentiality of the subjects, to the extent permitted by law and regulations. Any presentations of results from this study will only exhibit de-identified data.

Appendix 1 – Schedule of Assessments

Appendix 2 – AUDIT Questionnaire

The Alcohol Use Disorders Identification Test: Interview Version

Read questions as written. Record answers carefully. Begin the AUDIT by saying "Now I am going to ask you some questions about your use of alcoholic beverages during this past year." Explain what is meant by "alcoholic beverages" by using local examples of beer, wine, vodka, etc. Code answers in terms of "standard drinks". Place the correct answer number in the box at the right.

1. How often do you have a drink containing alcohol?
 
(0) Never [Skip to Qs 9-10] (1) Monthly or less (2) 2 to 4 times a month (3) 2 to 3 times a week (4) 4 or more times a week
 

	
6. How often during the last year have you needed a first drink in the morning to get yourself going after a heavy drinking session?
 
(0) Never (1) Less than monthly (2) Monthly (3) Weekly (4) Daily or almost daily
 

2. How many drinks containing alcohol do you have on a typical day when you are drinking?
 
(0) 1 or 2 (1) 3 or 4 (2) 5 or 6 (3) 7, 8, or 9 (4) 10 or more
 

	
7. How often during the last year have you had a feeling of guilt or remorse after drinking?
 
(0) Never (1) Less than monthly (2) Monthly (3) Weekly (4) Daily or almost daily
 

3. How often do you have six or more drinks on one occasion?
 
(0) Never (1) Less than monthly (2) Monthly (3) Weekly (4) Daily or almost daily
 
Skip to Questions 9 and 10 if Total Score for Questions 2 and 3 = 0
 

	
8. How often during the last year have you been unable to remember what happened the night before because you had been drinking?
 
(0) Never (1) Less than monthly (2) Monthly (3) Weekly (4) Daily or almost daily
 


4. How often during the last year have you found that you were not able to stop drinking once you had started?
 
(0) Never (1) Less than monthly (2) Monthly (3) Weekly (4) Daily or almost daily
 

	
9. Have you or someone else been injured as a result of your drinking?
 
(0) No (2) Yes, but not in the last year (4) Yes, during the last year
 

5. How often during the last year have you failed to do what was normally expected from you because of drinking?
 
(0) Never (1) Less than monthly (2) Monthly (3) Weekly (4) Daily or almost daily
 

	
10. Has a relative or friend or a doctor or another health worker been concerned about your drinking or suggested you cut down?
 
(0) No (2) Yes, but not in the last year (4) Yes, during the last year
 

Record total of specific items here

If total is greater than recommended cut-off, consult User's Manual.

Appendix 3 – SMAST Questionnaire

**SHORT MICHIGAN ALCOHOL SCREENING TEST
(SMAST)**

NAME: _____ Date: _____

The following questions concern information about your involvement with alcohol during the past 12 months. Carefully read each countymnt and decide if your answer is “YES” or “NO”. Then, check the appropriate box beside the question.

Please answer every question. If you have difficulty with a countymnt, then choose the respons that is mostly right.

These questions refer to the past 12 months only.	YES	NO
1. Do you feel that you are a normal drinker? (by normal we mean do you drink less than or as much as most other people.).....		
2. Does your wife, husband, a parent, or other near relative ever worry or complain about your drinking?.....		
3. Do you ever feel guilty about your drinking?.....		
4. Do friends or relatives think you are a normal drinker?.....		
5. Are you able to stop drinking when you want to?.....		
6. Have you ever attended a meeting of Alcoholics Anonymous (AA)?.....		
7. Has your drinking ever created problems between you and your wife, husband, a parent or other near relative?.....		
8. Have you ever gotten into trouble at work because of your drinking?.....		
9. Have you ever neglected your obligations, your family, or your work for two or more days in a row because you were drinking?.....		
10. Have you ever gone to anyone for help about your drinking?.....		
11. Have you ever been in a hospital because of drinking?.....		
12. Have you ever been arrested for drunken driving, driving while intoxicated, or driving under the influence of alcoholic beverages?.....		
13. Have you ever been arrested, even for a few hours, because of other drunken behaviors?.....		
* SMAST Score.....		

* See scoring instructions for correct scoring procedures.

Appendix 4 – Drinking History Questionnaire

CURRENT DRINKING

1. How many alcohol beverages do you consume per day on average?
2. How long have you used at this rate (in years)? _____
3. If Male: In the past 12 months, how many times have you had 5 or more drinks in a day? _____
4. If Female: In the past 12 months, how many times have you had 4 or more drinks in a day? _____
5. In the past 12 months, what is the largest amount of alcohol that you have had in one day?
 - a. Amount (in standard drinks, refer to chart): _____
 - b. Over what time period (in hours): _____
 - c. Type of beverage: _____
 - d. Brand: _____
6. Beverage preferences

✓	Beverage List	Preferred Manner of Drinking	Method of Preparation	Brand(s)
	Beer or ale			
	Brandy			
	Gin			
	Hard Cider			
	Liqueurs (Cordials)			
	Malt Liquor			
	Rum			
	Sake			
	Sparkling Wine			
	Special Fortified Wine			
	Tequila			
	Vodka			
	Whiskey			
	Red, Dry Wine			
	Red, Sweet Wine			
	Rose Wine			
	White, Dry Wine			
	White, Sweet Wine			
	Wine Coolers			
	Other (specify):			
	Other (specify):			

PAST DRINKING

1. At what age did you first have 1 or more drinks of alcohol? _____
2. How old were you when you first became intoxicated: _____ Never intoxicated
3. If applicable: At what age did drinking begin to have an effect on your life, which you did not approve of? When did drinking first become a problem for you?
Age when first problem: _____ Never a problem
4. Have you ever willingly quit drinking for a period longer than a few days? No Yes
5. How many past quit attempts have you had? _____ Not applicable, never attempted to quit
6. Have you ever been through alcohol treatment? No Yes
If Yes, provide details:
 - Inpatient: _____ year(s) of treatment
 - Outpatient: _____ year(s) of treatment
 - Alcoholics Anonymous (AA): _____ year(s) of treatment

